6.3 Dose Modifications for Mitoxantrone, Etoposide, Cytarabine

Table 5: Dose modifications for mitoxantrone, etoposide, cytarabine

Toxicity	Grade 1	Grade 2	Grade 3	Grade 4
Nausea	no change in dose			
Vomiting	no change in dose			
Diarrhea	no change in dose			
Neutropenia	no change in dose			
Thrombocytopenia	no change in dose			
Non-blistering	no change in	no change in	no change in dose	no change in dose

CONFIDENTIAL

This document is confidential. Do not disclose or use except as authorized.

rash	dose	dose		
Table 5: Dose modifications for mitoxantrone, etoposide, cytarabine				
Toxicity	Grade 1	Grade 2	Grade 3	Grade 4
Desquematting (blistering) rash	no change in dose	no change in dose	no change in dose	no change in dose
Neuropathy	no change in dose	no change in dose	no change in dose	no change in dose
Other clinically significant non-hematologic toxicity	no change in dose	no change in dose	Per physician discretion or institutional practice	Per physician discretion or institutional practice

7. ADVERSE EVENTS: LIST AND REPORTING REQUIREMENTS

An adverse event (AE) is any noxious, unintended, or untoward medical occurrence that may appear or worsen in a subject during the course of a study. It may be a new intercurrent illness, a worsening concomitant illness, an injury, or any concomitant impairment of the subject's health, including laboratory test values, regardless of etiology. Any worsening (i.e., any clinically significant adverse change in the frequency or intensity of a pre-existing condition) should be considered an AE. A diagnosis or syndrome should be recorded on the AE page of the CRF rather than the individual signs or symptoms of the diagnosis or syndrome. An overdose, accidental or intentional, whether or not it is associated with an AE, or abuse, withdrawal, sensitivity or toxicity to an investigational product should be reported as an AE. If an overdose is associated with an AE, the overdose and adverse event should be reported as separate terms. All subjects will be monitored for AEs during the study. Assessments may include monitoring of any or all of the following parameters: the subject's clinical symptoms, laboratory, pathological, radiological or surgical findings, physical examination findings, or findings from other tests and/or procedures.

All AEs will be recorded by the Investigator from the first dose of study treatment until 28 days after the last dose of lenalidomide and those SAEs made known to the investigator at any time thereafter that are suspected of being related to lenalidomide. AEs and serious adverse events (SAEs) will be recorded on the AE page of the CRF and in the subject's source documents. All SAEs must be reported to Celgene Drug Safety within 24 hours of the Investigator's knowledge of the event by facsimile, or other appropriate method, using the SAE Report Form, or approved equivalent form.

Adverse event (AE) monitoring and reporting is a routine part of every clinical trial. The following list of reported and/or potential AEs (Section 7.1) and the characteristics of an observed AE (Section 7.2) will determine whether the event requires expedited reporting **in addition** to routine reporting.

CONFIDENTIAL

This document is confidential. Do not disclose or use except as authorized.

Toxicity will be scored using CTCAE Version 4.03 for toxicity and adverse event reporting. A copy of the CTCAE Version 4.03 can be downloaded from the CTEP homepage (http://ctep.cancer.gov/protocolDevelopment/electronic_applications/ctc.htm#ctc_40). All appropriate treatment areas should have access to a copy of the CTCAE Version 4.03. All adverse clinical experiences, whether observed by the investigator or reported by the patient, must be recorded, with details about the duration and intensity of each episode, the action taken with respect to the test drug, and the patient's outcome. The investigator must evaluate each adverse experience for its relationship to MEC, relationship to lenalidomide, and for its seriousness. The investigator must appraise all abnormal laboratory results for their clinical significance. If any abnormal laboratory result is considered clinically significant, the investigator must provide details about the action taken with respect to the test drug and about the patient's outcome.

All adverse events experienced by participants will be collected from the time of the first dose of study treatment, through the study and until 28 days after the last dose of study treatment. Participants continuing to experience toxicity at the off study visit may be contacted for additional assessments until the toxicity has resolved or is deemed irreversible.

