5.6 Duration of Follow Up

Participants will be followed for at least 50 days after the start of protocol treatment. Participants will be followed for relapse and survival at 3 months after treatment, and then every

CONFIDENTIAL

This document is confidential. Do not disclose or use except as authorized.

six months until 3 years from start of treatment, including those patients who are removed from the study treatment prior to completing the 50 day toxicity period.

Participants removed from protocol therapy for unacceptable adverse event(s) will be followed until resolution or stabilization of the adverse event.

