7.3.2 Second Primary Malignancies

Second primary malignancies will be monitored as events of interest and must be reported as serious adverse events the subject is in. This includes any second primary malignancy, regardless of causal relationship to study drugs occurring at any time for the duration of the study, from the time of signing the ICD for at least 3 years from the date the last subject is enrolled into the study. Events of second primary malignancy are to be reported using the SAE report form and must be considered an "Important Medical Event" if no other serious criteria apply; these events must also be documented in the appropriate page(s) of the CRF (i.e., AE and SPM CRF) and subject's source documents. Documentation on the diagnosis of the second primary malignancy must be provided at the time of reporting as a serious adverse event (e.g., any confirmatory histology or cytology results, X-rays, CT scans, etc.).

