7.4 Expedited Adverse Event Reporting

All adverse event reports must include the patient number, age, sex, weight, severity/grade of reaction (e.g. mild, moderate, severe), relationship to drug attribution (e.g. probably related, unknown relationship, definitely not related), date and time of administration of study medications and concomitant medications, and medical treatment provided. The investigator is responsible for evaluating all adverse events to determine whether criteria for “serious” as defined above are present. The investigator is responsible for reporting adverse events to the Coordinating Center as described below.

Investigators **must** report to the Overall PI and Coordinating Center any serious adverse event (SAE) that occurs after the initial dose of study treatment, during treatment, or within 30 days of the last dose of treatment on the MedWatch 3500A Mandatory Reporting Form.

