7.4.1 Expedited Reporting to Celgene

For the purpose of regulatory reporting, Celgene Drug Safety will determine the expectedness of events of being related to lenalidomide based on the Investigator Brochure. In the United States, all determined unexpected serious adverse reactions (SUSARs) will be reported in an expedited manner in accordance with 21 CFR 312.32.

CONFIDENTIAL

This document is confidential. Do not disclose or use except as authorized.

Serious adverse events (SAE) are defined above. The investigator must inform the Coordinating Center in writing using a Celgene SAE form or MEDWATCH 3500A form of any SAE within 24 hours of being aware of the event. The written report must be completed and supplied to Celgene by facsimile within 24 hours. The initial report must be as complete as possible, including an assessment of the causal relationship between the event and the investigational product(s). Information not available at the time of the initial report (e.g., an end date for the adverse event or laboratory values received after the report) must be documented on a follow-up report. **A final report to document resolution of the SAE is required.** The Celgene tracking number (RV-CL-AML-PI006779) and the institutional protocol number should be included on SAE reports (or on the fax cover letter) sent to Celgene. A copy of the fax transmission confirmation of the SAE report to Celgene should be attached to the SAE and retained with the patient records.

The Coordinating Center will submit all SAE reports to Celgene Drug Safety immediately by facsimile, or other appropriate methods on behalf of the participating site.

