7.5 Routine Adverse Event Reporting

All Adverse Events **must** be reported in routine study data submissions to the Overall PI on the toxicity case report forms. **AEs reported through expedited processes (e.g., reported to the IRB, FDA, etc.) must also be reported in routine study data submissions.**

Celgene shall notify the Investigator via an IND Safety Report of the following information:

- Any AE suspected of being related to the use of drug in this study or in other studies that is both serious and unexpected.
- Any finding from tests in laboratory animals that suggests a significant risk for human subjects including reports of mutagenicity, teratogenicity, or carcinogenicity.

The Investigator shall notify his/her IRB/EC promptly of these new serious and unexpected AE(s) or significant risks to subjects.

The Investigator must keep copies of all pertinent safety information on file, including correspondence with Celgene and the IRB/EC.

[figure not shown]

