² All patients will have bone marrow examined at count recovery or at Day +35 +/- 3 days. Patient will be off treatment if persistent leukemia or need for further treatment. Patients who have count recovery within one week of the Day 35 marrow do not need a repeat bone marrow. Patients who have not experienced count recovery by Day 45 will have marrow at Day 45+/-3 days regardless of counts. Patients may have additional bone marrows performed as clinically indicated.

³The day 4 peripheral blood research sample should be obtained prior to the initiation of MEC chemotherapy (may be obtained before or after lenalidomide on that day).

⁴ Toxicity will be assessed from the time of first dose of study treatment through 30 days past the last dose of study treatment.

⁵Molecular testing (correlative 1) may be performed at the time of disease relapse and within 2 months of study enrollment, provided no intervening systemic chemotherapy has been administered (excluding hydroxyurea or 6MP).

^bSamples for optional correlative 4 may be collected at baseline prior to chemotherapy, and on day 3 of treatment (or day 2 or 4 if on a weekend, but prior to MEC administration).

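### Adverse-event recording ends at Day 38 and SAE reporting and toxicity assessment at Day 40 on the full schedule, but toxicity is to be evaluated to Day 50

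*Combined protocol and SAP*

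**What the plan says.** Section 7 gives two statements on general adverse events. The opening reads "All AEs will be recorded by the Investigator from the first dose of study treatment until 28 days after the last dose of lenalidomide", and then keeps SAEs suspected to be related to lenalidomide reportable without an end date. Later in the same section, collection runs "through the study and until 28 days after the last dose of study treatment".

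Two other places use 30 days. Section 7.4 requires reporting to the Overall PI and Coordinating Center of any SAE that "occurs after the initial dose of study treatment, during treatment, or within 30 days of the last dose of treatment". Table 6 footnote 4 in Section 10.4 says: "Toxicity will be assessed from the time of first dose of study treatment through 30 days past the last dose of study treatment". Section 7.4.1 asks for a written report "of any SAE within 24 hours of being aware of the event" and gives no period of its own.

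Three places use 50 days. Section 5.6 sets long-term follow-up "including those patients who are removed from the study treatment prior to completing the 50 day toxicity period". Section 10.4 follows patients for at least 50 days from the start of treatment, for response and adverse events. Section 13.1.1 makes every participant evaluable for toxicity until Day 50 or the start of other therapy. The same section holds the study if 3 or more of the first 10 patients have delayed count recovery beyond Day 45 or another unacceptable toxicity judged related to the regimen.

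Two routes run longer or have no stated end. Second malignancies are reported "from the time of signing the ICD for at least 3 years from the date the last subject is enrolled into the study" (Section 7.3.2). Section 7.5 requires all adverse events to "be reported in routine study data submissions to the Overall PI on the toxicity case report forms", with no end date.

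**The concern.** A recording rule that stops before the evaluation period ends leaves the last part of that period without systematic data. If a site follows the opening of Section 7, an empty adverse-event form for Days 39-50 could mean that nothing happened or that nobody was still recording. The trial has several sites. A site working from Section 10.4 or 13.1.1 could continue to Day 50 while another stops at Day 38, and each could point to protocol text in support.

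These are not quiet days. In the phase I study described in Section 2.4.1, the median time to neutrophil recovery was 30 days and to platelet recovery 34 days, so some patients had not recovered counts near the closing days. Section 7.4.4 exempts hematologic and routine chemotherapy toxicities from expedited reporting to the Overall PI and the DFCI IRB on the ground that the case report form still captures them. That form is the record whose end date is unclear.

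At stake are the completeness of the toxicity evaluation in Section 13.1.1 and, to a lesser degree, the part of the hold rule that covers unacceptable toxicities other than delayed count recovery.

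**Working it through.** **The plan's own figure.** The only computed figure attached to the toxicity evaluation is the 7% chance of a hold at a true rate of 10% (Section 13.1.1). With 10 patients and a trigger of 3 or more:

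P(X ≥ 3) = 1 − (0.3487 + 0.3874 + 0.1937) = 0.070.

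This agrees with the plan. It does not depend on any recording window.

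**Inputs.** Lenalidomide runs Days 1-10 and MEC Days 4-8 (Section 5.1). No lenalidomide is given after Day 10, even to make up missed doses (Section 6). Day 10 is therefore the last dose day on the full schedule.

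**End of each period for a last dose on Day 10.**

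| Place | Rule | Ends | Days left to Day 50 |
|---|---|---|---|
| Section 7, opening | last lenalidomide dose + 28 | 10 + 28 = Day 38 | 39-50: 50 − 38 = 12 |
| Section 7.4 (SAEs) | last dose + 30 | 10 + 30 = Day 40 | 41-50: 50 − 40 = 10 |
| Table 6, footnote 4 | last dose + 30 | Day 40 | 10 |
| Section 7, second statement | ambiguous | Day 38, or through the study | 12, or 0 |
| Sections 5.6, 10.4, 13.1.1 | 50 days | Day 50 | none |

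The Day 45 ± 3 visit (Days 42-48) falls wholly after both Day 38 and Day 40. Table 6 schedules counts, chemistry and an examination there.

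**Earlier stopping.** If the last study drug is lenalidomide on Day L, the shortfall is 50 − (L + 28) = 22 − L days under the 28-day rule and 50 − (L + 30) = 20 − L days under the 30-day rule. For L = 8 these are 14 and 12 days.

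The anchor also matters, because the opening of Section 7 counts from lenalidomide alone. Suppose lenalidomide stops on Day 5 and MEC finishes on Day 8:

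- Opening of Section 7: 5 + 28 = Day 33.
- Second statement, if read as a plain 28-day close: 8 + 28 = Day 36.
- Section 7.4 and Table 6 footnote 4: 8 + 30 = Day 38.

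All these shortfalls are upper limits, because evaluation under Section 13.1.1 ends sooner if other therapy starts.

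**What other routes cover.** Deaths to Day 50 are covered by Sections 11.2 and 11.5, and count recovery by Sections 10.2 and 11.1. Later SAEs suspected to be related to lenalidomide are covered by the opening of Section 7, and second malignancies by Section 7.3.2. What remains is mainly new non-serious events. SAEs not attributed to lenalidomide may also remain, if the 30 days in Section 7.4 limit Section 7.4.1 as well. The documents give no event rate for Days 39-50, so the number affected cannot be estimated.

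**The case against.** The strongest reply is that little of consequence is lost. Fatal events, count recovery and lenalidomide-related SAEs have their own routes, the secondary analyses are descriptive, and no design figure changes. That is true and limits the weight of the point. It does not remove the conflict, because Section 13.1.1 evaluates toxicity in general and not only those events.

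A second reply is that the later statement in Section 7 already extends collection through the study. That reading is open, so a reader should not treat that sentence as a clean Day 38 close. The sentence then adds the 28-day limit, however, and so does not settle which period governs. The opening of Section 7 and Table 6 footnote 4 have no such ambiguity.

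A reader might infer two further conflicts that the text does not support:

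- **Section 7.5 as a competing, open-ended window.** It says where adverse events are reported. Its silence on an end date does not contradict the periods stated earlier in Section 7.
- **Section 7.4.1 as a windowless SAE rule that contradicts Section 7.4.** It sits under 7.4 and is naturally read as a 24-hour deadline for SAEs already in scope. On that reading it cannot be relied on to catch every late SAE, which is why SAEs not attributed to lenalidomide may fall in the gap.

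Finally, the sections could be aligned by shortening Section 13.1.1 instead. That would remove the contradiction, but it fits the rest of the plan less well: three sections already use 50 days, treatment-related mortality is measured at 50 days, and the hold rule looks beyond Day 45.

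**Conclusion.** The conflict is real and should be corrected. On the full schedule, 12 days (39-50) of the stated toxicity period lie outside general adverse-event recording, and 10 days (41-50) lie outside SAE reporting under Section 7.4 and toxicity assessment under Table 6. The shortfall is longer if treatment stops early and shorter if other therapy starts before Day 50.

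This rests on counting the first dose as Day 1, on a last dose on Day 10, and on the opening of Section 7 being followed as written. If sites read the second statement in Section 7 as running through the study, the gap for general adverse events closes in practice, but the text still gives different end dates.

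A reader might go further and infer that safety data stop altogether at Day 38 or Day 40, or that the hold rule does not have its stated properties. The documents support neither. The routes listed above continue, the 7% is reproduced and unchanged, and the part of the hold rule based on count recovery has its own data. The effect on the other part is likely small. The sample size and the primary endpoint are not affected.

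**What to change.** Align both statements in Section 7, Section 7.4 and Table 6 footnote 4 with Sections 5.6, 10.4 and 13.1.1:

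- Use one recording period for AEs and SAEs: from first dose through Day 50 or the start of other therapy.
- Set a single minimum of 30 days after the last dose of any study drug, not lenalidomide alone. Since 10 + 30 = Day 40 at the latest, this minimum matters only when other therapy starts before it has run out.
- State in Section 7.4.1 that the 24-hour deadline applies to SAEs in that period.
- Keep the open-ended reporting of later SAEs suspected to be related to lenalidomide, and second-malignancy reporting under Section 7.3.2.

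The cost is protocol wording plus about 10-12 more days of adverse-event entry per full-schedule patient, and more where treatment stops early. The 50-day follow-up and the Day 45 visit are already planned. No dose, treatment rule or design figure changes.

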7.1 Expected Toxicities

7.1.1 Adverse Event List for Mitoxantrone

The most common adverse events include myelosuppression, fever and chills, alopecia, mucositis, and nausea and vomiting. Other commonly reported events include GI bleeding, malaise, fatigue, cardiomyopathy, anorexia and weakness. Other adverse events include cardiac arrhythmias, bleeding, abdominal pain, hepatitis, cough, shortness of breath, infertility, neuropathy and headache. Rare side effects include urticaria, rash, anaphylaxis, extravasation at the IV site, chest pain, pneumonitis, second cancers, and tachycardia.

7.1.2 Adverse Event List for Etoposide

The most common side effects are myelosuppression, mucositis, nausea, vomiting, and alopecia. Hypotension can occur during administration. Allergic reactions can also occur. Other adverse events include facial and tongue swelling, cough, back pain, abdominal pain, fatigue, fever, pulmonary fibrosis, rash, and hepatic toxicity. Rare toxicities include second cancers, rash, urticaria, itching, constipation, transient cortical blindness, optic neuritis, anaphylaxis, congestive heart failure, myocardial infarction, somnolence, and thrombophlebitis.

7.1.3 Adverse Event List for Cytarabine

The most common side effects include myelosuppression, nausea, vomiting, diarrhea, skin rash, mucositis, alopecia, fever, and reduced kidney function. Conjunctivitis may also occur. Other adverse events include diarrhea, urinary retention, confusion, jaundice, dizziness, and abdominal pain. Rare toxicities include pancreatitis, cough, and anaphylaxis.

CONFIDENTIAL

This document is confidential. Do not disclose or use except as authorized.

7.1.4 Adverse Event List for Lenalidomide

Most frequently reported adverse events reported during clinical studies with lenalidomide in oncologic and non-oncologic indications, regardless of presumed relationship to study medication include: leukopenia, neutropenia, febrile neutropenia, granulocytopenia, lymphopenia, pancytopenia, anemia, thrombocytopenia, blurred vision, diarrhea, abdominal pain, toothache, constipation, dyspepsia, nausea, vomiting, asthenia, fatigue; edema, pyrexia, chills, pneumonia, bronchitis, upper respiratory tract infection, urinary tract infection, erysipelas, gastroenteritis, Herpes simplex, Herpes zoster, Influenza, lower respiratory tract infection, sinusitis, sepsis, bacteremia, nasopharyngitis, pharyngitis, rhinitis, weight loss; decreased appetite, hyperglycemia, hypokalemia, hypocalcemia, hypophosphatemia, hypomagnesemia, hyponatremia, pain in extremity, pain in limb, arthralgia, back pain, bone pain, muscle spasms, musculoskeletal pain, muscle cramp, chest pain, myalgia, dizziness, dysgeusia, headache; cataracts, hypoesthesia; neuropathy, peripheral neuropathy, peripheral sensory neuropathy, tremor, cough, dyspnea, epistaxis, pulmonary embolism, deep vein thrombosis, dry skin, pruritus, rash, hypersensitivity (in uncommon category), depression, insomnia and recently vertigo.

Complete and updated adverse events are available in the Investigational Drug Brochure

7.2 Adverse Event Characteristics

7.2.1 CTCAE term (AE description) and grade

The descriptions and grading scales found in the revised NCI Common Terminology Criteria for Adverse Events (CTCAE) version 4.03 will be utilized for AE reporting. All appropriate treatment areas should have access to a copy of the CTCAE version 4.03. A copy of the CTCAE version 4.03 can be downloaded from the CTEP web site

http://ctep.cancer.gov/protocolDevelopment/electronic_applications/ctc.htm.

- Grade 1 = Mild – transient or mild discomfort; no limitation in activity; no medical intervention/therapy required
- Grade 2 = Moderate – mild to moderate limitation in activity, some assistance may be needed; no or minimal medical intervention/therapy required
- Grade 3 = Severe – marked limitation in activity, some assistance usually required; medical intervention/therapy required, hospitalization is possible
- Grade 4 = Life-threatening – extreme limitation in activity, significant assistance required; significant medical intervention/therapy required, hospitalization or hospice care probable
- Grade 5 = Death - the event results in death

